Appendix 16: Study Details Specific to RO7247669 600 mg +Tira Arm

improved progression-free survival (PFS = 10.1 months) over nivolumab (PFS = 4.6 months). The incidence of Grade 3 or 4 treatment-related adverse events was 18.9% in patients that received the nivolumab and relatlimab combination and 9.7% in patients that received nivolumab alone (Tawbi et al. 2022).

An ongoing Phase I/II study is evaluating the safety, tolerability, and clinical activity of combination treatment with the anti-PD-1 monoclonal antibody spartalizumab and the anti-LAG-3 monoclonal antibody LAG525 in patients with advanced solid tumors. Preliminary anti-tumor activity was observed during the Phase I dose-escalation portion of the study, including durable responses in 2 of 5 patients with triple-negative breast cancer (TNBC) and in 2 of 8 patients with mesothelioma. Analyses of tumor biopsies from the TNBC cohort also showed a trend of conversion from an immune-cold to an immune-activated phenotype. Common adverse events, i.e., adverse events reported in ≥10% of patients, included fatigue (18%), diarrhea (15%), and nausea (12%). The incidence of Grade 3–4 adverse events was 8% for both the combination (n=121) and monotherapy (n=119) arms (Hong et al. 2018).

An ongoing, first-in-human, dose-escalation, and dose-expansion Phase I study is evaluating the safety, tolerability, and clinical activity of the anti-PD-1/LAG-3 dual affinity re-targeting protein (DART®) bsAb MGD013 in patients with advanced solid tumors and hematologic malignancies. During the dose-escalation phase of the study, the maximum tolerated dose (MTD) was not reached, and the safety profile was consistent with anti-PD-1 monotherapy. During the dose-expansion phase, anti-tumor activity was observed in patients with TNBC (n=23; ORR, 4.3%; disease control rate [DCR], 39.1%), CPI-naive NSCLC (n=14; ORR, 14.3%; DCR, 64.3%), and epithelial ovarian cancer (n=23; ORR, 8.7%; DCR, 52.2%). Expression of LAG-3 and an IFN-γ gene signature at baseline was associated with objective responses (Luke et al. 2020). Clinical studies evaluating MGD013 as monotherapy and in combination with anti-HER-2 agents are ongoing.

A16-2.4.1 Study NP41300

Study NP41300 is an ongoing, first-in-human, dose-escalation, dose-expansion Phase I study to evaluate the safety, pharmacokinetics, and therapeutic activity of the anti-PD-1/LAG-3 bsAb RO7247669 as a single-agent in patients with locally advanced and/or metastatic solid tumors. Part A, the dose-escalation phase of the study, is designed to determine the MTD and/or recommended dose for expansion (RDE) of RO7247669. Part B of the study is designed to evaluate the anti-tumor activity of RO7247669 at the MTD or RDE in tumor-specific expansion cohorts.

As of the data cut-off date, 1 March 2022, RO7247669 was well tolerated in the patients enrolled in Part A of the study. No unexpected safety concern associated with RO7247669 was identified. No dose-limiting toxicities (DLTs) were observed up to the

Appendix 16: Study Details Specific to RO7247669 600 mg +Tira Arm

maximum dose tested (2100 mg every 2 weeks [Q2W]), and no MTD was identified. The maximum dose of 2100 mg was determined to be the recommended dose for the dose-expansion phase (Part B) of Study NP41300. As of the data cutoff date, 1 March 2022, 83 patients received treatment in Part B.

As of the data cut-off date, 1 March 2022, the DCR in Part A of the study was 51.4% (18 of 35 evaluable patients), and the ORR was 17.1% (6 of 35 patients). Among the patients treated with the proposed dose of 2100 mg Q2W, 7 of 13 patients had a best response of stable disease or better (DCR=53.8%), including 4 patients with a confirmed partial response (PR, ORR=30.8%). Besides the confirmed partial responses (cPR) observed at the RDE, there were 2 cPRs at the 600 mg dose level (ORR =50.0%).

As of the data cut-off date, 1 March 2022, in Part B of the study the DCR was 48.3% (28 of 58 patients) and the ORR was 5.2% (3 of 58 patients) among patients of the study treated at the RDE of 2100 mg Q2W (Cohorts B1, B2, and B3). Within patients treated with 600 mg Q2W (Cohort B5), the DCR was 40% (4 of 10 patients), and the ORR was 10% (1 of 10 patients). Among patients treated with 600 mg Q3W, the DCR was 28.6% (2 of 7 patients) and the ORR was 14.3% (1 of 7 patients).

Refer to the RO7247669 Investigator's Brochure for additional details on all ongoing and planned clinical studies.

A16-2.5 CLINICAL STUDIES OF TIRAGOLUMAB

Tiragolumab is currently under investigation in two ongoing clinical studies in patients with solid tumors (Studies GO30103 and GO40290) and in one clinical study in patients with hematological malignancies (Study GO41036).

A16-2.5.1 Study GO30103

Study GO30103 is a first-in-human, open-label, multicenter, global, dose-escalation/dose-expansion Phase I study. It was designed to evaluate the safety, tolerability, and pharmacokinetics of tiragolumab as a single agent (Phase Ia) and in combination with atezolizumab (Phase Ib) in patients with locally advanced, recurrent, or metastatic incurable tumors, including urothelial cancer, renal cell cancer, NSCLC, head and neck squamous cell carcinoma, esophageal cancer, colorectal cancer (CRC), gastric cancer, cholangiocarcinoma, and triple-negative breast cancer.

As of the clinical cutoff date of 2 December 2020, a total of 236 patients had been enrolled in Study GO30103. Forty-two patients were enrolled in the Phase Ia portion of the study to receive single-agent tiragolumab, and 217 patients were enrolled in the Phase Ib portion of the study to receive tiragolumab in combination with atezolizumab. The latter group included 23 patients who crossed over from the Phase Ia portion of the study.

Appendix 16: Study Details Specific to RO7247669 600 mg +Tira Arm

The best observed response with tiragolumab monotherapy in the Phase Ia portion was prolonged stable disease in 8 of 42 patients, with some patients, including 1 patient with CRC, experiencing a decrease in tumor size.

In the Phase Ib portion, complete response was observed in 4 of 217 patients at tiragolumab dose levels of 400 mg (n=3/48) and 600 mg (n= 1/104) in combination with 1200 mg atezolizumab. Partial response was observed in 27 of 217 patients at tiragolumab dose levels of 30 mg (n=2/13), 400 mg (n=6/48), and 600 mg (n=18/104) in combination with 1200 mg atezolizumab, including two patients who crossed over from the Phase Ia portion at the 600 mg dose level. Stable disease was observed in 53 of 217 patients at tiragolumab dose levels of 2 mg (n=1/8), 8 mg (n=3/12), 30 mg (n= 2/13), 100 mg (n= 3/8), 400 mg (n=12/48), 600 mg (n=25/104), and 1200 mg (n=7/24) in combination with 1200 mg atezolizumab, including 8 patients who crossed over from the Phase Ia portion of the study (2 patients at 8 mg, 1 patient at 30 mg, 2 patients at 100 mg, and 3 patients at 400 mg).

As of 2 December 2020, safety data were available for 235 safety-evaluable patients in Study GO30103. A total of 42 patients were treated in the Phase Ia portion with tiragolumab as a single agent (2 mg to 1200 mg), while 216 patients were treated in the Phase Ib portion with tiragolumab at dose levels of 2 mg to 1200 mg in combination with atezolizumab at 1200 mg, including 23 patients who crossed over from the Phase Ia portion to the Phase Ib portion.

Tiragolumab was tolerated across all administered dose levels both as a single agent and in combination with atezolizumab. The MTD was not reached, and the maximum administered dose was 1200 mg. No DLTs or clear dose-related trends in the incidence of adverse events were observed. Grade ≥ 3 adverse events, regardless of attribution to the study drug(s), were reported in 16 patients (38.1%) and 113 patients (52.3%) in the Phase Ia and Phase Ib portions, respectively. There were 14 reported deaths in the Phase Ia portion of the study, including 12 deaths due to malignant neoplasm progression, 1 death due to gastrointestinal hemorrhage in the context of progressive disease, and 1 death due to hepatic failure. The death due to hepatic failure was considered by the investigator to be related to study drug. One hundred eighteen deaths were reported in the Phase Ib portion of the study. This included 111 deaths due to progressive disease (31 cases were reported as adverse events during the adverse event reporting period and coded as malignant neoplasm progression or neoplasm malignant), 2 deaths due to pulmonary embolism, 1 death due to esophageal hemorrhage, 1 death due to sepsis, 1 death due to septic shock, 1 death due to COVID-19, and 1 death due to upper airway obstruction. Treatment-related serious adverse events were reported in 1 patient in the Phase Ia portion (hepatic failure) and in 10 patients (4.6%) in the Phase Ib portion. No patient discontinued study treatment due to adverse events in the Phase Ia portion of Study GO30103. Adverse events

Appendix 16: Study Details Specific to RO7247669 600 mg +Tira Arm

leading to treatment discontinuation were reported in 12 patients in the Phase Ib portion of the study, with a Grade 4 cardiac tamponade, a Grade 4 pneumonitis, and one event of Grade 2 arthralgia considered by the investigator to be related to the study drug(s). Adverse events of special interest were reported in 5 patients (11.9%) in the Phase Ia portion and 82 patients (38.0%) in the Phase Ib portion of the study.

Overall, tiragolumab as a single agent or in combination with atezolizumab has been well tolerated, adverse events have been manageable, and the safety profile has been observed to be consistent across different solid tumor indications.

A16-2.5.2 Study GO40290

Study GO40290 is a Phase II, randomized, blinded, placebo-controlled study of tiragolumab plus atezolizumab compared with placebo plus atezolizumab in patients with previously untreated locally advanced unresectable or metastatic PD-L1-positive NSCLC (defined as tumor proportion score [TPS] $\geq 1\%$).

As of the primary clinical cutoff date of 30 June 2019, 135 patients with a PD-L1 TPS $\geq 1\%$ were included in the intent-to-treat (ITT) population and were randomly assigned to receive tiragolumab plus atezolizumab ($n=67$) or placebo plus atezolizumab ($n=68$). As of the primary analysis, 47.8% of patients in the tiragolumab plus atezolizumab group versus 27.9% of patients in the placebo plus atezolizumab group were still receiving study treatment in the ITT population. In the TPS $\geq 50\%$ population, 65.5% of patients in the tiragolumab plus atezolizumab group versus 24.1% of patients in the placebo plus atezolizumab group were still receiving study treatment.

In all randomized patients, the combination of tiragolumab plus atezolizumab improved the co-primary endpoints of investigator-assessed ORR and progression-free survival (PFS) compared to placebo plus atezolizumab, with median follow-up of 5.9 months. ORR for tiragolumab plus atezolizumab was 31.3% (95% CI: 19.5, 43.2) compared with placebo plus atezolizumab which was 16.2% (95% CI: 6.7, 25.7).

Investigator-assessed median PFS for tiragolumab plus atezolizumab was 5.4 months (95% CI: 4.2 months, not reached) compared with placebo plus atezolizumab which was 3.6 months (95% CI: 2.7 months, 4.4 months), with a stratified hazard ratio (HR) of 0.57 (95% CI: 0.37, 0.90). Investigator-assessed PFS was improved in the tiragolumab plus atezolizumab group over the placebo plus atezolizumab group (unstratified HR = 0.33; 95% CI: 0.15, 0.72; median PFS not reached vs. 3.9 months, respectively).

As of 2 December 2020, 67 safety-evaluable patients in the tiragolumab plus atezolizumab arm in Study GO40290 were treated with a median of 8 doses of tiragolumab and atezolizumab (range: 1–38) for a median of 5.0 months (range: 0.03–26.0). In the placebo plus atezolizumab arm, 68 safety-evaluable patients

Appendix 16: Study Details Specific to RO7247669 600 mg +Tira Arm

were treated with a median of 5 doses of placebo and atezolizumab (range: 1–37) for a median of 2.8 months (range: 0.03–26.3).

As of 30 June 2020, in the Phase II randomized, placebo-controlled Study GO40290, a total of 135 safety-evaluable patients were administered either tiragolumab (600 mg recommended Phase II/III dose) in combination with atezolizumab or placebo in combination with atezolizumab. The safety profile of tiragolumab plus atezolizumab was similar to that of placebo plus atezolizumab- for all-grade adverse events (98.5% vs. 97.1%), Grade ≥ 3 adverse events (53.7% vs. 50.0%), serious adverse events (47.8% vs. 39.7%), and adverse events leading to treatment discontinuation (13.4% vs. 11.8%). Adverse events of special interest were reported in 58.2% of patients in the tiragolumab plus atezolizumab arm and in 32.4% of patients in the placebo plus atezolizumab arm. One death due to Epstein-Barr virus (EBV) reactivation and possible secondary hemophagocytic lymphohistiocytosis (HLH) was reported in this study, which was considered by the investigator to be related to the study drugs.

Overall, tiragolumab in combination with atezolizumab has been well tolerated, adverse events have been manageable, and the safety profile seems to be consistent as reported across different solid tumor indications.

Refer to the Tiragolumab Investigator's Brochure for additional details on all ongoing and planned clinical studies.

A16-2.6 BENEFIT—RISK ASSESSMENT

The combination of RO7247669 and tiragolumab is currently being tested in this study. The combination of atezolizumab and tiragolumab has a favorable emergent benefit–risk profile, and early clinical experience with RO7247669 suggest a safety profile comparable to that of atezolizumab and other PD-1/PD-L1 blocking antibodies (Appendix 12). The combination of nivolumab (anti–PD-1) and relatlimab (anti–LAG-3) improved PFS over nivolumab alone as first-line therapy in melanoma patients in the Phase III Relativity-047 study (Tawbi et al. 2022), which supports the expected benefit from RO7247669 (anti–PD-1/anti–LAG-3 bispecific therapy) in combination with tiragolumab. Taking into account the potentially synergistic mechanisms of action of RO7247669 and tiragolumab, as well as their manageable and tolerable safety profiles (see Section A16-5), combination treatment with these two agents has promise as a potential therapy in solid tumors such as melanoma.

For the evaluation of the impact of the COVID-19 pandemic on the benefit–risk assessment, please refer to Section 1.3.

Appendix 16: Study Details Specific to RO7247669 600 mg +Tira Arm

A16-3 RATIONALE FOR DOSE AND SCHEDULE FOR RO7247669 600 mg +TIRA ARM

A16-3.1 RATIONALE FOR RO7247669 600 mg DOSE AND SCHEDULE

RO7247669 will be administered at a fixed dose of 600 mg every 3 weeks (Q3W) (600 mg on Day 1 of each 21-day cycle). A fixed dosing regimen of 600 mg Q3W was selected based on available clinical pharmacokinetic, efficacy, and safety data from Study NP41300. During the dose-escalation Part A of the study, RO7247669 was well tolerated, and no specific safety concern associated with RO7247669 was identified. No DLT up to the highest dose of 2100 mg Q2W was observed, and no MTD was identified. Anti-tumor activity, as measured by radiographic partial responses, was observed starting at a dose of 600 mg Q2W. The pharmacokinetics of RO7247669 were dose linear within the dose range tested in Study NP41300. Greater than 90% occupancy of peripheral PD-1 and LAG3 receptors on CD8⁺ cells was observed at 50 mg of RO7247669 and was sustained at all higher doses (unpublished Roche data on file). Further modelling of intratumoral PD-1 and LAG3 target engagement using estimated target properties was performed. A dose regimen of 600 mg Q3W was selected for this study (BO43328) to ensure that the majority of participants have at least 90% PD-1 and LAG3 tumor receptor saturation by RO7247669, irrespective of intratumoral spatial heterogeneity and intersubject variability. A dose greater than 600 mg would not be expected to result in further clinical activity.

In study NP41300, persistent anti-drug antibodies (ADAs) formed in approximately 18% of the total population and the incidence rate was not dose dependent. An impact on exposure was observed at 50, 150 and 300 mg; therefore, 600 mg will be used in Study BO43328 to minimize the risk of a loss in exposure due to ADAs.

In addition, RO7247669 was well tolerated in both the dose-range finding studies and Good Laboratory Practice (GLP) monkey toxicology studies up to the highest dose evaluated (100 mg/kg). Toxicology findings were consistent with the findings in cynomolgus monkey studies of marketed CPIs. In the current study (BO43328), the safety evaluation of the first 6 patients enrolled in the RO7247669 2100 mg arm was completed with no safety signals identified.

The supporting data for the selected dose can be found in the current RO7247669 Investigator's Brochure.

A16-3.2 RATIONALE FOR TIRAGOLUMAB DOSE AND SCHEDULE

Tiragolumab will be administered at a fixed dose of 600 mg IV Q3W (600 mg on Day 1 of each 21-day cycle).

Appendix 16: Study Details Specific to RO7247669 600 mg+Tira Arm

The fixed dose of 600 mg IV Q3W was selected on the basis of available clinical pharmacokinetic, efficacy, and safety data from the combined Phase Ia/Phase Ib Study GO30103 with single-agent tiragolumab or tiragolumab in combination with atezolizumab. In the Phase Ia portion of the study with tiragolumab as a single agent, the MTD was not reached, and no DLTs were observed during dose-escalation. As of the clinical cutoff date, anti-drug antibodies (ADAs) to tiragolumab were rare in the Phase Ia or Phase Ib portions across all dose levels. Complete occupancy of peripheral TIGIT receptors on CD4⁺, CD8⁺, and NK cells was observed beginning at 30 mg of tiragolumab in both the Phase Ia and Phase Ib portions of the study and remained sustained at all higher doses (unpublished Roche data on file).

Prolonged stable disease was observed in patients in the Phase Ia portion of the study at tiragolumab doses beginning at 400 mg. In the Phase Ib portion of the study with tiragolumab plus atezolizumab, the MTD was not reached. Anti-tumor activity, as measured by radiographic partial responses, was observed across doses for tiragolumab beginning at 30 mg and ranging up to 600 mg in combination with 1200 mg atezolizumab. Refer to the Tiragolumab Investigator's Brochure for additional details.

A16-4 MATERIALS AND METHODS SPECIFIC TO RO7247669 600 mg+TIRA ARM

A16-4.1 TREATMENT IN RO7247669 600 mg+TIRA ARM

A16-4.1.1 Formulation, Packaging, and Handling

A16-4.1.1.1 RO7247669

The RO7247669 drug product will be supplied by the Sponsor as a 50 mg/mL concentrate for solution for infusion.

For information on the formulation, packaging, and handling of RO7247669, refer to the pharmacy manual and the RO7247669 Investigator's Brochure.

A16-4.1.1.2 Tiragolumab

The tiragolumab drug product will be supplied by the Sponsor as a 60 mg/mL concentrate for solution for infusion.

For information on the formulation, packaging, and handling of tiragolumab, refer to the pharmacy manual and the Tiragolumab Investigator's Brochure.

A16-4.1.2 Dosage, Administration, and Compliance

Patients in the RO7247669 600 mg+Tira arm will receive treatment for 2 cycles (6 weeks) as outlined in [Table A16-1](#) until surgery, or until unacceptable toxicity or loss of clinical benefit, whichever occurs first (see [Section 3.1.2](#) for details). It is recommended that treatment be initiated no later than 7 days after randomization.

Appendix 16: Study Details Specific to RO7247669 600 mg+Tira Arm

Table A16-1 Treatment Regimen for RO7247669 600 mg+ Tira Arm

Cycle Length	Dose, Route, and Regimen (drugs listed in order of administration)
21 days	
• RO7247669 600 mg IV on Day 1 of each cycle• Tiragolumab 600 mg IV on Day 1 of each cycle

Tira=tiragolumab.

Refer to the pharmacy manuals for detailed instructions on drug preparation, storage, and administration.

Medication errors should be noted on the Study Drug Administration electronic Case Report Form (eCRF). Cases of accidental overdose or medication error, along with any associated adverse events, should be reported as described in Section 5.3.5.12.

No safety data related to overdosing of RO7247669 or tiragolumab are available to date.

A16-4.1.2.1 RO7247669

RO7247669 will be administered by IV infusion at a fixed dose of 600 mg on Day 1 of each 21-day cycle.

Administration of RO7247669 will be performed in a monitored setting where there is immediate access to trained personnel and adequate equipment and medicine to manage potentially serious reactions. For anaphylaxis precautions, see [Appendix 8](#). RO7247669 infusions will be administered per the instructions outlined in [Table A16-2](#).

Appendix 16: Study Details Specific to RO7247669 600 mg +Tira Arm

Table A16-2 Administration of First, Second, and Subsequent RO7247669 Infusions

First and Second Infusion	Subsequent Infusions

• No premedication is permitted prior to the first RO7247669 infusion.• Vital signs (respiratory rate, pulse rate, blood pressure, pulse oximetry, and temperature) should be measured within 60 minutes prior to the infusion and recorded on the eCRF.• For the first infusion, RO7247669 should be infused over 60 (± 10) minutes.• After the infusion of RO7247669, the patient begins a 60-minute observation period.• For the second infusion, RO7247669 should be infused over 30 (± 10) minutes if the first infusion was tolerated without an IRR.• If clinically indicated, vital signs should be measured every 15 (± 5) minutes during the infusion and at 30 (± 10) minutes after the infusion. Record on the eCRF in case of abnormalities.• Patients should be informed about the possibility of delayed post-infusion symptoms and instructed to contact their study physician if they develop such symptoms.	
• If the patient experienced an IRR with any previous infusion, premedication with antihistamines, antipyretics, and/or analgesics may be administered for subsequent doses at the discretion of the investigator.• Vital should be measured within 60 minutes prior to the infusion and recorded on the eCRF.• RO7247669 should be infused over 30 (± 10) minutes if the previous infusion was tolerated without an IRR.• If the patient tolerated the previous infusion of RO7247669 well without infusion-associated adverse events, the observation period may be reduced to 30 minutes.• If the patient experienced an IRR with the previous infusion or if clinically indicated, vital signs should be measured every 15 (± 5) minutes during the infusion and at 30 (± 10) minutes after the infusion. Record on the eCRF in case of abnormalities.

eCRF=electronic Case Report Form; IRR=infusion-related reaction.

For patients who experience a Grade ≥ 2 infusion-related reaction (IRR), premedication with paracetamol 500–1000 mg orally [PO] or IV and diphenhydramine 25–50 mg PO or IV (or an alternative histamine H₁/₂ antagonist at an adequate dose) is required prior to subsequent infusions. In case of Grade 3 or 4 IRRs related to study treatment, the patient should be permanently discontinued from the study treatment.

Guidelines for medical management of IRRs for RO7247669 are provided in Section [A16-5.1.2.1](#).

No dose modification for RO7247669 is allowed. Guidelines for treatment interruption or discontinuation because of toxicities are provided in Section [A16-5.1.2.2](#).

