Appendix 14: Study Details Specific to RO7247669 2100 mg+Tira Arm (Cohorts 1 and 2)

A14-4 MATERIALS AND METHODS SPECIFIC TO RO7247669 2100 mg +TIRA ARM

A14-4.1 TREATMENT IN RO7247669 2100 mg+TIRA ARM

A14-4.1.1 Formulation, Packaging, and Handling

A14-4.1.1.1 RO7247669

The RO7247669 drug product will be supplied by the Sponsor as a 50 mg/mL concentrate for solution for infusion.

For information on the formulation, packaging, and handling of RO7247669, refer to the pharmacy manual and the RO7247669 Investigator's Brochure.

A14-4.1.1.2 Tiragolumab

The tiragolumab drug product will be supplied by the Sponsor as a 60 mg/mL concentrate for solution for infusion.

For information on the formulation, packaging, and handling of tiragolumab, refer to the pharmacy manual and the Tiragolumab Investigator's Brochure.

A14-4.1.2 Dosage, Administration, and Compliance

Patients in the RO7247669 plus tiragolumab (RO7247669+Tira 2100 mg) arm will receive treatment as outlined in [Table A14-1](#). Patients in Cohort 1 will receive treatment for 2 cycles (6 weeks) until surgery, or until unacceptable toxicity or loss of clinical benefit, whichever occurs first (see [Section 3.1.2](#) for details).

Patients in Cohort 2 will receive treatment until unacceptable toxicity or loss of clinical benefit as determined by the investigator after an integrated assessment of radiographic and biochemical data, local biopsy results (if available), and clinical status (e.g., symptomatic deterioration such as pain secondary to disease) (see [Section 3.1.2](#) for details). It is recommended that treatment be initiated no later than 7 days after randomization (Cohort 1) or enrollment (Cohort 2).

Table A14-1 Treatment Regimen for RO7247669 2100 mg+Tira Arm

Cycle Length	Dose, Route, and Regimen (drugs listed in order of administration)
21 days	
• RO7247669 2100 mg IV on Day 1 of each cycle ^a• Tiragolumab 600 mg IV on Day 1 of each cycle

Tira = tiragolumab.

^a After the safety run-in has been completed, the Sponsor may explore lower doses (e.g., 1200 mg and 600 mg).

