Appendix 15: Study Details Specific to RO7247669 600 mg Arm

Table A15-3 Guidelines for Management of Patients Who Experience Adverse Events in RO7247669 600 mg Arm

Event	Action to Be Taken
IRRs, anaphylaxis, and hypersensitivity reactions	
General guidance	
 For anaphylaxis precautions, see Appendix 8. For severe hypersensitivity reactions, permanently discontinue RO7247669. For suspected CRS, see Appendix 9 for guidance on supportive care. Determine tryptase concentration and IgE titer if clinical presentation of IRR suggests an anaphylactic or hypersensitivity reaction (hives, obstructive shortness of breath, urticaria, other histamine associated symptoms) and/or if the first IRR or CRS (\geqGrade 2) is observed at the second infusion. If tryptase and/or IgE are elevated, collect a second sample for IgE/trypatase analysis at least 48 hours after the onset of the reaction to rule out the possibility of an anaphylactic reaction.
IRR to RO7247669, Grade 1 or 2	
 Slow infusion to \leq50% or interrupt infusion. Give supportive treatment. Patients should be treated with acetaminophen/paracetamol and an antihistamine, such as diphenhydramine, if they have not been administered in the last 4 hours. IV fluids (e.g., normal saline) may be administered as clinically indicated. For bronchospasm, urticaria, or dyspnea, antihistamines, oxygen, corticosteroids (e.g., 100 mg IV prednisolone or equivalent), and/or bronchodilators may be administered per institutional practice. Upon symptom resolution, infusion may resume (if interrupted) at 50% starting rate. The infusion must remain at the lower rate resulting in symptom resolution for the remainder of the infusion. For Grade 2 IRRs, subsequent doses of RO7247669 should be administered with pre-medication, including acetaminophen/paracetamol and an antihistamine such as diphenhydramine. For Grade 2 wheezing or urticaria, patient must also be pre-medicated prior to subsequent doses (as described above). If symptoms recur with the same or greater severity following the slower or interrupted infusion, the infusion must be stopped immediately. No further RO7247669 will be administered for the cycle.

CRS=cytokine-release syndrome; GI=gastrointestinal; HLH=hemophagocytic lymphohistiocytosis; IRR=infusion-related reaction; MAS=macrophage activation syndrome.

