Appendix 16: Study Details Specific to RO7247669 600 mg+Tira Arm

Table A16-4 Guidelines for Management of Patients Who Experience Adverse Events in the RO7247669 600 mg+Tira Arm (cont.)

Event	Action to Be Taken
IRRs, anaphylaxis, and hypersensitivity reactions (cont.)	
IRR to RO7247669 and/or tiragolumab Grade 1	
 Reduce infusion rate to half the rate being given at the time of event onset. After the event has resolved, the investigator should wait for 30 minutes while delivering the infusion at the reduced rate. If the infusion is tolerated at the reduced rate for 30 minutes after symptoms have resolved, the infusion rate may be increased to the original rate.
IRR to RO7247669 and/or tiragolumab Grade 2	
 Interrupt infusion. Administer aggressive symptomatic treatment (e.g., oral or IV antihistamine, anti-pyretic medication, glucocorticoids, epinephrine, bronchodilators, oxygen, IV fluids). After symptoms have resolved to baseline, resume infusion at half the rate being given at the time of event onset. For subsequent infusions, consider administration of oral premedication with antihistamines, antipyretic medications, and/or analgesics and monitor closely for IRRs.
IRR to RO7247669 and/or tiragolumab, Grade 3 or 4	
 Stop infusion. Administer aggressive symptomatic treatment (e.g., oral or IV antihistamine, anti-pyretic medication, glucocorticoids, epinephrine, bronchodilators, oxygen, IV fluids). Permanently discontinue RO7247669 and tiragolumab and contact the Medical Monitor.
Pulmonary, hepatic, GI, endocrine, ocular, immune-mediated myocarditis, CRS, pancreatic, dermatologic, neurologic, immune-mediated meningoencephalitis, renal, myositis, HLH, MAS, and systemic immune activation	
 Guidelines for the management of these events are provided in Appendix 9.

CRS=cytokine-release syndrome; GI=gastrointestinal; HLH=hemophagocytic lymphohistiocytosis; IRR=infusion-related reaction; MAS=macrophage activation syndrome.

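### In the RO7247669 600 mg + Tira arm, a Grade 1 or 2 reaction to the first RO7247669 infusion does not by itself trigger 15-minute vital signs at the second, and premedication after Grade 2 is required in one place but optional in another

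*Combined protocol and SAP*

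**What the plan says.** Section A16-4.1.2 states that patients "will receive treatment for 2 cycles", and Table A16-1 gives RO7247669 on Day 1 of each. Table A16-2 is nevertheless titled "Administration of First, Second, and Subsequent RO7247669 Infusions". It has two columns, one for the first and second infusions together and one for later infusions.

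In the shared column the vital-sign line begins "If clinically indicated, vital signs should be measured every 15" (±5) minutes. In the later-infusion column it begins "If the patient experienced an IRR with the previous infusion or if clinically indicated, vital signs should be measured every 15" (±5) minutes. The line allowing discretionary premedication after an earlier reaction is also only in the later-infusion column.

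Below the table, premedication after a reaction of Grade 2 or higher "is required prior to subsequent infusions". The Grade 2 row of Table A16-4 reads: "For subsequent infusions, consider administration of oral premedication with antihistamines, antipyretic medications, and/or analgesics and monitor closely for IRRs".

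**The concern.** The second infusion is the only re-exposure to RO7247669 in this arm, so it is where a rule for patients who have already reacted has to work. As laid out, the explicit rule governs no infusion at all, and what remains is the investigator's judgement.

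Section A16-5.1.3 lists infusion reactions among the overlapping toxicities of the two drugs, and Section A16-2.6 says the combination is still being tested in this study. Yet on this one line the written rule is weaker than in Appendix 15, where the same 600 mg dose is given alone.

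The premedication conflict concerns the same patients. A site working from the management table could reasonably omit something that the dosing section makes mandatory. Nothing here touches an efficacy result; the issue is patient safety on a dosing day and consistent conduct across sites.

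**Working it through.** The plan gives no figure to reproduce. The check is a count and a side-by-side reading.

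**Infusions.** 2 cycles × 1 infusion per cycle = 2 infusions. The later-infusion column starts at the third, so it governs 0 infusions in this arm.

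**Where the post-reaction vital-sign trigger sits for RO7247669.**

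| Setting | Planned infusions | Column covering infusion 2 | Earlier reaction is a trigger at infusion 2 |
|---|---|---|---|
| Appendix 12, Table A12-2 | 2 | Second | Yes |
| Appendix 15, Table A15-2 | 2 | Second | Yes |
| Appendix 14 Cohort 1, Table A14-2 | 2 ("Patients in Cohort 1 will receive treatment for 2 cycles") | First and second | No |
| Appendix 14 Cohort 2, Table A14-2 | Open-ended | First and second | No |
| Appendix 16, Table A16-2 | 2 | First and second | No |

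The trigger reaches the second infusion in 2 of the 5 settings, or 2 of the 4 with exactly two infusions. Both are single-agent arms; the settings without it all add tiragolumab. In Cohort 2 the trigger takes effect from the third infusion.

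**Grades affected.** A Grade 3 or 4 reaction ends treatment (text below Table A16-2, and Table A16-4), so only Grades 1 and 2 can lead to a second infusion. For Grade 1, Table A16-4 says nothing about later infusions. For Grade 2 it asks for close monitoring but gives no interval.

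**Premedication after a Grade 2 reaction.**

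| Appendix | Text below the infusion table | Management table |
|---|---|---|
| 12 | Required | To be given (Table A12-3) |
| 15 | Required | To be given (Table A15-3: "For Grade 2 IRRs, subsequent doses of RO7247669 should be administered with pre-medication") |
| 14 | Required | To be considered (Table A14-4) |
| 16 | Required | To be considered (Table A16-4) |

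Text and management table agree in Appendices 12 and 15 and conflict in Appendices 14 and 16.

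**Readings at stake.** Under the rule, vital signs are taken every 15 minutes during the infusion (counting the one at its end) and once 30 minutes after it.
- 30-minute infusion: 30/15 + 1 = 3 sets.
- 60-minute infusion: 60/15 + 1 = 5 sets.

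The 30- to 60-minute range is an assumption, because no RO7247669 table gives a duration for a second infusion after a reaction. The documents shown give no reaction rate for RO7247669, so the number of patients affected cannot be estimated.

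**The case against.** The strongest reply is that clinical indication alone is an accepted standard in this protocol. The tiragolumab tables (A13-3, A14-3 and A16-3) use only that wording after the first infusion, with no separate trigger for an earlier reaction, and their columns are laid out correctly. An investigator facing a patient who has just reacted would very likely regard that as an indication.

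This stands as a limit on the harm. It does not explain the difference for RO7247669: Tables A12-2 and A15-2 name an earlier reaction and clinical indication as two alternatives, so for this drug the sponsor did not leave the matter wholly to judgement.

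A reader might also infer that a patient who reacted is re-exposed with no vital signs after the pre-infusion set, or that Appendix 16 is less protective overall than Appendix 15. The documents do not support either. RO7247669 is given before tiragolumab, and Table A16-3 requires vital signs within 60 minutes before tiragolumab. If the RO7247669 observation period is completed first, that reading follows the RO7247669 infusion. Table A16-2 also keeps 60 minutes of observation at the second infusion, whereas the 30 minutes in Table A15-2 is tied to a first infusion without a reaction, and no period is stated otherwise.

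Finally, the pointer in A16-4.1.2.1 to A16-5.1.2.1, a tiragolumab risk section, might be read as leaving sites without guidance. It does not: that section itself sends the reader to Table A16-4. The wrong pointers are clerical.

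**Conclusion.** The point holds as a minor drafting fault in operative safety instructions. In Appendix 16 the post-reaction vital-sign trigger applies to none of the two infusions given, and Appendix 14 has the same gap at the second infusion in both cohorts. Premedication after Grade 2 is stated in two incompatible ways in both appendices.

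It is tempting to put all of this down to a third-infusion column left in a two-infusion arm. Cohort 2 rules that out as the full explanation: it does reach later infusions, yet its second infusion has the same gap because that infusion shares a column with the first.

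The size is about 3 to 5 sets of vital signs per patient with a Grade 1 or 2 first reaction, on the assumed infusion length, plus possible omission of premedication after Grade 2. The conclusion rests on the part of the protocol shown. Table A16-5 cites Section 4.5.4 for vital signs; that section is not shown and could contain a general rule that closes the monitoring gap.

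**What to change.** 1. Recast Table A16-2 with one column for the first infusion and one for the second, as in Table A15-2. Put the post-reaction vital-sign line and the discretionary premedication line in the second column, and keep the 60-minute observation.
2. In Table A14-2, make the post-reaction lines apply to the second infusion in both Cohort 1 and Cohort 2.
3. In the Grade 2 rows of Tables A16-4 and A14-4, make premedication required, to match the text below Tables A16-2 and A14-2. Do not restrict it to the drug thought to have caused the reaction: the existing requirement names no drug, and A16-5.1.4.2 advises attributing events generally to both agents.
4. As clerical tidying, redirect the two pointers at the end of A16-4.1.2.1 to A16-5.1.4.3 (management of reactions) and A16-5.1.4.2 (treatment interruption).

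The cost is edits to two infusion tables, two management-table rows and two cross-references. Sites take the extra readings only in patients who reacted, and the premedication is already mandatory in the text. No visit or analysis is added.
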